1. Incorporate mandated Clinical Trial Facilitation Group (CTFG) guidance to clarify the requirement of FSH measurements to confirm postmenopausal status;
2. Include contingency measures for a regional or national emergency, as declared by a governmental agency;
3. Update the inclusion/exclusion criteria, prohibited concomitant medications and AESI according to the new available data from ongoing amcenestant studies;
4. Optimize the PK assessment time points for amcenestant.

Protocol amendment summary of changes table

Section # and Name	Description of Change	Brief Rationale
1.3 Schedule of Activities (SOA): notes of FSH test & 5.1 Inclusion criteria I04 b)	Updated the protocol verbiage to reflect serial FSH measurements are required to confirm postmenopausal status for the patients who have received hormonal replacement therapy but have discontinued this treatment and in the absence of amenorrhea >12 months.	In line with the recommended Clinical Trial Facilitation Group (CTFG) guidance dated 2014, multiple FSH measurements (at least two) to confirm postmenopausal state should be conducted before including women in the absence of amenorrhea >12 months.
1.3 Schedule of Activities (SOA): footnote d; & 8.6.1 Tumor biopsy Section 8.8.1 Protein Biomarkers	Added Cyclin D1 in the exploratory protein biomarker panel to be tested by IHC in tumor tissues.	To complement data on impact of amcnestant and letrozole on cell cycle arrest in addition to Ki67, since Cyclin D1 is regulated by ER.
3 Objectives and endpoints: Table 1; & 8.6.1 Tumor biopsy	Added Complete Cell Cycle Arrest (CCCA) as an exploratory endpoint to further assess impact on proliferation; and added digital assessment of protein biomarkers.	To add some additional tools to evaluate impact on proliferation, and to explore increased reproducibility and objective measurement of protein expression.
1.3 Schedule of Activities (SOA)	Removed PK sampling on Day 1 and Day 7, and added PK sampling on Day 15.	To optimize the PK sample collection time points. So that an on-site visit could be changed to a remote visit whenever possible (especially during pandemic).
5.1 Inclusion criteria I01	Added "or country's legal age of majority if the legal adult age is >18 years old".	To adapt some local country's law.

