Viral serologies	X						Viral serologies include hepatitis A antigen or IgM hepatitis A antibody, HBs antigen or hepatitis B viral DNA, hepatitis C antibody or quantitative hepatitis C viral (HCV) ribonucleic acid (RNA).
Single 12-lead ECG	X						See Section 8.2.3 for details.
Triplicate ECG		X		X			Electronic records of triplicate ECG are required at pre-dose on D1 and at pre-dose and 3h post-dose on D14. See Section 8.2.3 for details.
Vital signs	X	(X)	X	X			These assessments will be repeated within 1 day prior to the first dosing of IMP if abnormal or if screening assessment >7 days of D1. See Section 8.2.2 for details.
Patient diary distribution		X					
Patient diary review			X	X			
Amcenestant administration 400 mg QD		Continuous once a day (QD)					Study treatment should be taken in the morning. Study treatment duration is planned for 14 days, and should not exceed 14 days. IMP will be dispensed at the study site visits on D1. On D1 and D14, IMP will be taken on-site after fasting tests and pre-dose assessment. See Section 6.1 for details.
Amcenestant administration 200 mg QD		Continuous once a day (QD)					
Letrozole administration		Continuous once a day (QD)					

Procedure ^a	Screening	Treatment Period (14 days)			Surgery ^c	Post treatment safety follow-up period	Notes
	up to 14 days before randomization	D1 ^b	D7 (±2)	D14	D15 (+1)	30 (±7) days after last IMP intake	
Tumor Biopsy ^d	X				X		Participant selection is based on the biopsy at diagnosis analyzed in a local lab. A new core-cut biopsy (baseline sample) should be performed prior to the first dosing of IMP, as well as a core-cut biopsy from surgery specimen or new core-cut biopsy after the last IMP intake for study purpose. Alternatively, tissue from the diagnostic biopsy may be used for the baseline sample if certain criteria are fulfilled. Baseline and post-treatment biopsy will be centrally examined. See Section 8.6.1 for details.
Tumor size by ultrasound	X			X			Measurement of tumor size using ultrasound at screening (baseline) and on D14. At screening, tumor size assessed by ultrasound will also be used for inclusion criteria. See Section 8.1.2 for details.

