Pathological tumor (pT) stage, the pathological node (pN) stage, pCR and ECOG response assessment, Preoperative Endocrine Prognostic Index (PEPI)					X		Pathological tumor (pT) stage, the pathological node (pN) stage, and pCR results will be collected from the local pathologist's report following examination of tissue (breast and nodes) removed at the time of surgery and reported in eCRF. ECOG response will be assessed by the investigator according to ECOG response criteria. See Section 8.1.1 and Section 8.1.3 for details.
AE/SAE review	←=====→						AEs of new onset as well as worsening of baseline signs and symptoms are to be reported from the signing of the informed consent to 30 (±7) days following the last IMP intake. All SAEs, and non-serious AEs of special interest, and non-serious AEs related to IMP still ongoing at the post treatment safety follow-up visit, will be followed until resolution, stabilization, the event is otherwise explained, or the participant is lost to follow-up. See Section 8.3 for details.
Concomitant medication	←=====→						The period of collection of concomitant medications extends from the signing of the informed consent to 30 (±7) days following the last IMP intake. See Section 6.5 for details.

Procedure ^a	Screening	Treatment Period (14 days)			Surgery ^c	Post treatment safety follow-up period	Notes
	up to 14 days before randomization	D1 ^b	D7 (±2)	D14	D15 (+1)	30 (±7) days after last IMP intake	
Genetic sample (plasma for cfDNA)		X		X			cfDNA sample collected on D1 and D14. See Section 8.7 for details.
Genetic sample (saliva for reference DNA)		X					Saliva will be collected on D1 to extract DNA which will be used as a normal reference for the mutation analysis. See Section 8.7 for details
Genetic sample (blood for DMET genotyping)		X					Blood sample will be collected on Day 1 for amcenestant treatment arms only. See Section 8.7 for details
Amcenestant PK				X	X		PK sampling is planned only for amcenestant treatment arms. D14: Pre-dose (P00), T3h post dose (P01) D15: T24h post dose (P02) after last administration of amcenestant (D14) When PK and triplicate ECG are scheduled at the same time, PK sample will be taken just after ECG recording. Participants will take IMP on-site on days of PK sampling. See Section 8.5 for details.

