AE = adverse event, cfDNA = cell free DNA, DMET = Drug metabolizing enzymes and transporters, eCRF = electronic case report form, ECG = electrocardiogram, ECOG PS = Eastern Cooperative Oncology Group Performance Status, IMP = investigational medicinal product, IRT = Interactive response technology, pCR = pathological complete response, PEPI = Preoperative Endocrine Prognostic Index, PK = pharmacokinetic, pN = pathological node, pT = pathological tumor, QD = once daily, SAE = serious adverse event

- a Procedure:** Assessments to be performed prior to study treatment administration unless otherwise indicated. Informed consent should be signed before any study specific procedures. It can be signed more than 14 days prior to randomization. Screening time indicates in which timeframe exams used to support eligibility have to be done prior to randomization. All the tests or procedures scheduled on D1 should be done at predose time unless otherwise stated.
- b D1** refers to the day the participant receives the initial dose of study treatment which will be a single administration of amcenestant 400 mg or 200 mg QD, or letrozole 2.5 mg QD.
- c Surgery:** The date of surgery should be fixed before randomization takes place. The time between first IMP administration and surgery should be of 14 days and the last dose is planned to be taken the day before surgery. Surgery should be done 1 day after the last IMP administration; however this could exceptionally be extended to a maximum of 48h after last IMP administration. In case of a longer unexpected surgery delay (>48 hours from last IMP administration), all efforts should be done to perform a tumor biopsy no more than 48 hours of last IMP administration.

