8 STUDY ASSESSMENTS AND PROCEDURES

Study procedures and their timing are summarized in the SoA ([Section 1.3](#)). Protocol waivers or exemptions are not allowed.

- Adherence to the study design requirements, including those specified in the SoA, is essential and required for study conduct.
- All screening evaluations must be completed and reviewed to confirm that potential participants meet all eligibility criteria. If the participant fails to meet the exclusion criteria related to laboratory assessments at Screening, the laboratory assessments may be performed one more time to assess eligibility.
- Repeat or unscheduled samples may be taken for safety reasons or for technical issues with the samples.
- Additional safety tests (eg, ECG, hematology, coagulation, and clinical chemistry) can be performed whenever clinically indicated.
- The date of surgery should be fixed before randomization takes place. The time between first IMP administration and surgery should be of 14 days. Surgery should be done 1 day after the last IMP administration; however this could exceptionally be extended to a maximum of 48 hours after the last IMP administration. In case of a longer unexpected surgery delay (>48 hours from last IMP administration), all efforts should be done to perform a tumor biopsy no more than 48 hours of last IMP administration.
- The IMP dose will be taken on-site after fasting tests and pre-dose assessment on Day 1 and Day 14.
- For a regional or national emergency declared by a governmental agency, contingency measures are included in Appendix 14: Contingency Measures for a regional or national emergency that is declared by a governmental agency.

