When possible, the focus should be on Investigational Medicinal Product (IMP) administration and safety blood collection (eg, biochemistry and hematology). However, all efforts should be made to perform the measurements of key parameters for efficacy endpoints (eg, tumor assessments) ([Section 8](#)). The deviations from the study protocol (eg, treatment delay, omission, tests not performed...) should be documented in the source document and collected in the appropriate pages of the eCRF.

Procedures to be considered in the event of a regional or national emergency declared by a governmental agency:

- If onsite visits are not possible, remote visits (eg, with home nurses, home health vendor, etc) may be planned for the collection of possible safety and/or efficacy data (eg safety assessments, efficacy assessments especially the tumor assessment, PRO).
- If onsite visits are not possible visit windows may be extended for assessment of safety and/or efficacy data that cannot be obtained remotely.
- Use of local clinic or laboratory locations may be allowed.

Contingencies implemented due to emergency will be documented.

The impact of the regional or national emergency declared by a governmental agency on study conduct will be summarized (eg, study discontinuation or discontinuation/delay/omission of the intervention due to the emergency). Any additional analyses and methods required to evaluate the impact on efficacy (eg, missing data due to the emergency) and safety will be detailed in the SAP.

For a regional or national emergency declared by a governmental agency, contingency procedures may be implemented for the duration of the emergency. The participant or their legally authorized representative should be verbally informed prior to initiating any changes that are to be implemented for the duration of the emergency (eg, study visit delays/treatment extension, use of local labs) ([Section 10.1.3](#)).

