2.3.3 Per-protocol (PP) population

PP population is defined as all participants from the mITT population without relevant deviation(s), which could affect the evaluation of the study drug on the primary endpoint. PP population will be used for sensitivity analysis of the primary endpoint.

Major or critical deviations leading to exclusion from the per-protocol population is defined as follows:

- **Informed consent procedure:**
 - Patient does not sign study informed consent or informed consent is signed after study procedure
- **Inclusion/exclusion criteria:**
 - Patient without histological and cytological proven diagnosis of invasive breast adenocarcinoma
 - The localized breast cancer is not eligible for upfront breast conservative surgery or upfront mastectomy
 - Patient is not postmenopausal as per age and criteria defined in the protocol
 - The breast tumor size is less than 10 mm in short axis measured by ultrasound
 - Patient doesn't have a primary tumor positive in ER or non-overexpressing HER2 per protocol definition
 - Ki67 level is lower than 15% at diagnosis from immunohistochemistry of the tumor based on local laboratory results
 - Ki67 level is lower than 15% at baseline based on central laboratory results
 - Prior anti-cancer treatment was completed <1 year prior to inclusion into this trial
 - Patient is not female
 - Recent use of hormone replacement therapy (last dose \leq 30 days prior to randomization)

- **Concomitant medications/therapy**
 - Protocol prohibited therapy/medication/vaccine administered
- **IMP management:**
 - Patient receives ≤ 10 days or ≥ 16 days of the IMP treatment
- **Randomization procedure:**
 - IMP dispensed without Randomization
 - IMP actually dispensed to the subject is different from the IMP allocated

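### The PK sampling note, read literally, makes Day 15 a dosing day in the amcenestrant arms only and contradicts the protocol's 14-day treatment limit

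*Protocol*

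**What the plan says.** The PK row of the protocol's Schedule of Activities (Section 1.3) has marks under Day 14 and under the surgery column, Day 15 (+1). Its note limits the row to the experimental arms ("PK sampling is planned only for amcenestant treatment arms"). It lists a pre-dose and a 3-hour sample on Day 14 and a 24-hour sample on Day 15, counted from the last administration, which it places on Day 14. It then states, with no exception for Day 15: "Participants will take IMP on-site on days of PK sampling".

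Day 15 became a PK day with Amendment 02, whose summary of changes reads: "Removed PK sampling on Day 1 and Day 7, and added PK sampling on Day 15".

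The other dosing statements are:

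- Section 1.3, administration rows: "Study treatment duration is planned for 14 days, and should not exceed 14 days". The same note gives Day 1 and Day 14 as the on-site dosing days.
- Section 1.3, footnote c: "the last dose is planned to be taken the day before surgery". Section 4.1 says the same.
- Section 8: "The IMP dose will be taken on-site after fasting tests and pre-dose assessment on Day 1 and Day 14".

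Two SAP provisions bear on the point. Section 2.4.7.1 sets the time windows that decide which concentrations enter the descriptive statistics. It names pre-dose samples on Day 7 and Day 14, and a 2-to-4-hour window for 3-hour post-dose samples on Day 14 and Day 15. Section 2.3.3 removes a participant from the per-protocol population for 10 or fewer, or 16 or more, "days of the IMP treatment".

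**The concern.** The PK sentence is an instruction that a site can act on, and it sits in the table that sites work from. Taken at its word, it calls for an on-site dose on every PK day, which now includes the planned day of surgery. The rest of the protocol does not allow for that dose.

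Three things would follow if a site acted on it:

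- An unplanned investigational dose would be given around surgery, in a study that Section 2.3 describes as having no direct benefit for the patient.
- It could happen only in the amcenestrant arms. The post-treatment Ki67 biopsy, which supplies the primary endpoint, is taken from the excised tissue at surgery (Section 8.6.1). If the dose came before the biopsy, the time from last dose to biopsy would differ systematically between the experimental arms and letrozole.
- If the dose came before the Day 15 blood draw, that sample would no longer be a 24-hour concentration.

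The SAP would not reliably expose the problem. Its Day 15 window describes a sample that could exist only after a Day 15 dose, and its per-protocol rule tolerates a 15th day.

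**Working it through.** **Day count, reproducing the plan's own figure.** Inputs: once-daily dosing from Day 1, a 14-day maximum, and surgery 14 days after the first dose (Section 1.3, footnote c).

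- Doses from Day 1 to Day 14: 14 − 1 + 1 = 14, as stated.
- Surgery: Day 1 + 14 days = Day 15.
- Day before surgery: 15 − 1 = Day 14, the day the PK note gives for the last administration.
- Day 14 + 24 hours = Day 15, the scheduled 24-hour sample.

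The explicit dosing statements therefore agree with one another and with the definition of the Day 15 sample.

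**Literal reading of the PK sentence.** The PK days are Day 14 and Day 15. Dosing on both gives 14 + 1 = 15 doses with amcenestrant and 14 with letrozole; 15/14 = 1.07, about 7% more.

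**Statements this conflicts with:**

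| Statement | Place in protocol | With a Day 15 dose |
|---|---|---|
| Last administration on Day 14 | 1.3, same PK note | Contradicted |
| 14-day maximum | 1.3, administration rows | Exceeded by one day |
| On-site dosing on Day 1 and Day 14 | 1.3 and 8 | A further on-site day |
| Last dose the day before surgery | 1.3 footnote c, 4.1 | Contradicted when surgery is on Day 15 |

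If surgery moves to Day 16 within the allowed window, the last row is no longer contradicted, but the first three still are.

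**Likely origin (inference).** Day 1 and Day 7, the PK days that Amendment 02 removed, are dosing days. The sentence did no harm there. It became a problem once a day after the end of treatment was added.

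**SAP windows.** A sample drawn 24 hours after the Day 14 dose lies outside the 2-to-4-hour window. No other window for Day 15 is given, so under Section 2.4.7.1 as it reads the scheduled sample has no route into the summary table. The Day 7 window refers to a sample no longer in the protocol schedule. The sentence ends in a semicolon, so a separate Day 15 window may have been intended, but none is stated.

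**SAP backstop.** The per-protocol exclusions are 10 days or fewer and 16 or more. Fifteen days exceeds the protocol maximum of 14 and is retained. Relative dose intensity (SAP 2.4.4) would not flag it either: for the 400 mg arm, cumulative dose over duration is (15 × 400)/15 = 400 mg/day, or 100% of plan.

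**The case against.** The strongest reply is that no careful site would dose on Day 15. The PK note itself places the last administration on Day 14, just before the sentence in question. Section 7.1.1 sets the duration at 14 days, and Section 6.6 does not allow doses omitted for toxicity to be made up after that period. Returned capsules are counted at the Day 14 visit (Section 6.4), and returned drug is not to be re-dispensed (Section 6.3), so a Day 15 dose would need supply outside the described process. This stands. It shows that a 15th dose was probably not intended and that the probability of one is low. It does not remove the contradiction.

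A reader might go further and infer that the plan gives the amcenestrant arms a 15th dose, and so builds in an exposure imbalance. The documents do not support that. It requires reading one sentence against its own note and against every explicit dosing statement.

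A reader might also try to size the bias from the pharmacokinetics in Section 4.3. That does not work. Elimination is described as biphasic. The terminal half-life of about 20 hours is preliminary and comes from single doses in healthy women. The quoted volume (about 120 L) and clearance (about 14–15 L/h) would give 0.693 × 120/14.5 = 5.7 hours in a one-compartment model. The documents give no time from a Day 15 dose to the biopsy and no link between a dose hours before biopsy and Ki67 after two weeks of treatment.

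On the SAP side, the PK windows are analysis rules, not dosing instructions. The per-protocol set serves sensitivity analysis; the main analysis uses the mITT population. Duration of exposure is already summarised by arm (SAP 2.4.4), so 15-day exposure would be visible there. The SAP also states that enrolment ended early and that no hypothesis test will be done on the primary endpoint. All of this limits the consequence. The mismatch with the protocol remains.

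**Conclusion.** The contradiction is real and is one of wording. One unrestricted sentence in the PK note makes Day 15 a dosing day for amcenestrant only, and it disagrees with its own note, the 14-day maximum, the named on-site dosing days and the last-dose timing. The weight of the text is against a planned 15th dose.

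If a site followed the sentence, the difference would be 15 doses against 14 for that participant, about 7%, and only in the experimental arms. The consequences for the biopsy interval and the 24-hour sample assume that the dose comes before the biopsy and the blood draw. The documents do not say how often this could occur, and any effect on Ki67 cannot be derived from them.

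It still merits correction. It concerns dosing on the planned day of surgery, it is confined to the experimental arms of an open-label comparison, and the SAP's Day 15 window describes the sample inconsistently with the protocol. The per-protocol limit is a secondary matter.

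**What to change.** 1. **Protocol, Section 1.3, PK note.** Reconcile the on-site dosing sentence with the administration rows, footnote c, Section 4.1 and Section 8, so that all of them name the on-site dosing day or days consistently. Which day or days those are is for the sponsor's clinical team to settle. Cost: one sentence and no added procedure, though a protocol amendment needs ethics approval (Section 10.1.1).
2. **SAP, Section 2.4.7.1.** Reconcile the sampling windows with the protocol's PK schedule: the Day 7 entry, the 3-hour entry on Day 15 and the absent window for the 24-hour sample. Cost: one sentence, to be settled before database lock.
3. **SAP, Section 2.3.3 (secondary).** Reconcile the upper exposure limit for the per-protocol population with the protocol's stated maximum duration, or explain the difference. Cost: one line. The downside is that a few participants may leave the per-protocol sensitivity set; the mITT analysis is unaffected.

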2 INTRODUCTION

Amcenestant is a potent, orally bioavailable, and selective ER inhibitor that belongs to the SERD class of compounds. Amcenestant antagonizes the binding of estradiol to ER and also promotes the transition of ER to an inactive conformation that leads to up to 98% receptor degradation at nanomolar concentrations in cellular assays. Amcenestant is a superior and broader ER degrader than all known SERD competitors. These dual properties of amcenestant translate in a deeper inhibition of ER pathways and a more effective anti-proliferative activity in ER-dependent breast cancer cell lines driven by mutant or wild type ER compared to fulvestrant.

Amcenestant is currently in clinical development in metastatic breast cancer; first in human (TED14856; NCT03284957) study started in September 2017 and the dose escalation of amcenestant single agent is completed, dose expansion is ongoing.

A detailed description of the chemistry, pharmacology, efficacy and safety of amcenestant is provided in the Investigator's Brochure.

